#### Blood Collection

Any blood that is remaining after the analysis is completed will be stored frozen indefinitely at BIMDC for use in future studies. The sample will remain de-identified, but be labeled with the unique subject code. Information related to the subject's diagnosis, treatment, and study results will be retained and possibly used in future analysis and more information becomes identified regarding functional bowel disorders. PHI related to the stored samples will not be used in the future analysis and will be kept on BIDMC's secure server. Any samples that may be shared with collaborators will contain the subject code, but will not have any identifiable information or PHI.

#### Placebo Tablets

Placebo tablets are matching film-coated [white] tablets that contain standard FDA approved excipients that are used for Mytesi tablets and are identical in size, shape and weight. They will be provided and produced by the manufacturer of Mytesi (crofelemer).

### **B. Statistical Considerations**

#### ***Sample Size Justification:***

This study aims to recruit 120 subjects until 80 subjects are enrolled. This sample size is based on a 85% power calculation assuming placebo response is 40%.

#### ***Data Analysis:***

All continuous variables will be tested for normality using the Shapiro-Wilk test. Normally distributed continuous data will be presented as mean ( $\pm$  SD) and will be compared pre-and post- interventions using paired Student's t-test. Continuous data which are not normally distributed will be presented as median (range) and compared using Wilcoxon signed-rank test. Proportions will be expressed as percentages and compared using chi-square test or fisher exact test as appropriate.

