### B1. PURPOSE OF PROTOCOL

The primary objectives of this study are:

- To evaluate the clinical response of patients with diarrhea to crofelemer relative to placebo.
- To evaluate the overall safety and tolerability of crofelemer in the treatment of diarrhea.

The secondary objective of this study is assess whether improvement in bowel function with crofelemer is more effective in subjects without evidence of bile acid malabsorption (i.e., elevated C4 level).

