#### Visit 2 (Day 0)

- Adverse event assessment
- Vitals (weight, blood pressure, temperature, heart rate)
- Subjects who meet all conditions for study entry will be randomized into the 4-week double-blind treatment phase. Subjects will be randomized (1:1) to receive crofelemer 125 mg BID or placebo BID for 4 weeks. Approximately 80 patients will be randomly assigned (in a 1:1 ratio) to 125mg crofelemer bid vs. placebo.
- Subjects will continue to complete daily diary assessments of their bowel symptoms and use of loperamide during the 4-week treatment period via RedCap.

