#### **Questionnaires/Efficacy Assessments**

Throughout the study subjects will be required to access their electronic diary every day via RedCap, preferably at the same time each day, to record bowel symptoms and rescue medication use.

- Bristol Stool Score (BSS)  
Patients will be asked to rate the BSS most representative of the past 24 hours. The patient-reported BSS consistency score is based on a 1 to 7 scale where 1 corresponds to a hard stool and 7 corresponds to watery diarrhea.
- Frequency, Urgency and Incontinence  
Patients will be asked to record the number of bowel movements, number of incontinence episodes and the number of urgency episodes over the past 24 hours.
- Diarrhea - Adequate Relief  
Once per week patients will be asked whether they have experienced adequate relief of their diarrheal symptoms. The IBS-adequate relief (IBS-AR) score is a dichotomous single item used to assess adequate relief of IBS symptoms.
- Diarrhea - Quality of Life  
Patients will be asked to assess the impact of their IBS-like symptoms on their quality of life using the IBS-Quality of Life instrument (Patrick et al, 1998). The IBS-QoL will be completed at the study center at all visits. The IBS-QoL will be completed at the beginning of the applicable study visits before all other evaluations, especially discussion of AEs or the patient's medical condition.
- Worst Abdominal Pain Score  
Patients will be asked to rate their worst abdominal pain in the past 24 hours. The patient-reported worst abdominal pain will be recorded on a 0 to 10 scale, where 0 corresponds to no pain and 10 corresponds to worst imaginable pain.
- Abdominal Discomfort Score  
Patients will be asked to rate their abdominal discomfort in the past 24 hours. The patient-reported abdominal discomfort will be recorded on a 0 to 10 scale, where 0 corresponds to no discomfort and 10 corresponds to worst imaginable discomfort.
- Abdominal Bloating Score

Patients will be asked to rate their abdominal bloating in the past 24 hours. The patient-reported abdominal bloating will be recorded on a 0 to 10 scale, where 0 corresponds to no bloating and 10 corresponds to worst imaginable bloating.

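### A normality pre-test picks the test and summary for each continuous outcome, and both branches are within-patient, so no crofelemer-versus-placebo estimate is planned; one baseline-adjusted between-arm model should be fixed in advance

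*Combined protocol and SAP*

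**What the plan says.** The rule is in section B3.B, Data Analysis. It opens with "All continuous variables will be tested for normality using the Shapiro-Wilk test". Variables that pass are summarised by mean and SD and "will be compared pre-and post- interventions using paired Student's t-test". For the rest, "Continuous data which are not normally distributed will be presented as median (range) and compared using Wilcoxon signed-rank test". Proportions follow a separate route, to a chi-square or Fisher exact test.

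The text does not give the significance level of the normality test or the visit. Nor does it say whether the test is applied by arm or pooled, or to raw values or to changes. No other section names a model or a between-arm test for a continuous outcome.

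The rule therefore covers the continuous measures under Questionnaires/Efficacy Assessments: Bristol Stool Score (BSS), pain, discomfort, bloating, IBS-QoL, and daily counts of bowel movements as well as the "number of incontinence episodes and the number of urgency episodes over the past 24 hours".

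The first primary objective in B1 is "To evaluate the clinical response of patients with diarrhea to crofelemer relative to placebo". On numbers, Visit 2 says "Approximately 80 patients will be randomly assigned (in a 1:1 ratio) to 125mg crofelemer bid vs. placebo", which is 40 per arm.

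**The concern.** There are two faults in one rule.

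1. **The data choose the effect measure.** A mean change and a rank shift are different quantities. Which one is reported depends on a significance test of the outcome data, so it can change from outcome to outcome and visit to visit. If normality is checked within each arm, it can also differ between the arms of one outcome.

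2. **Neither branch compares the arms.** The paired t-test and the signed-rank test both ask whether patients changed from their own baseline. Such change also includes placebo response, regression to the mean after selection on loose stools, and natural fluctuation. The trial has a placebo arm to remove these, but the rule never subtracts it. The remaining route to a treatment claim is to set two within-arm p-values side by side, which is not a test of the treatment difference. Baseline is collected but never used as a covariate.

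At stake is whether the continuous outcomes can support any statement about crofelemer relative to placebo.

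**Working it through.** **The plan's own figure.** The sample size is 80, from 85% power and a 40% placebo response. The crofelemer response rate and alpha are not stated, so 80 cannot be reproduced. At 40 per arm and an assumed two-sided 0.05, 85% power needs a crofelemer response of about 73%. That calculation concerns a proportion, and this point does not depend on it. Only n = 40 per arm is carried forward.

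**Assumptions.** The documents give no SD, baseline-post correlation r or level for the Shapiro-Wilk test. Assumed: SD 1 at both times, r = 0.5 unless varied, and a 0.05 level for all tests. Simulations used 4,000 runs, except where noted.

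**Step 1: within-arm tests with no drug effect.** The variance of change is 2(1-r) = 2(0.5) = 1. With an equal 0.3 SD improvement in both arms, the standardised shift in one arm is 0.3 × √40 = 1.90. The normal approximation to the chance of a significant result is Φ(1.90 - 1.96) = Φ(-0.06) ≈ 0.47. Simulating the whole rule (Shapiro-Wilk on the change, then paired t or signed-rank) gives 0.46. The chance that the arms disagree is about 2 × 0.46 × 0.54 = 0.50; the simulation gives 0.49. By symmetry, half of these (0.49/2 ≈ 0.25) have crofelemer significant and placebo not.

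| Equal improvement in both arms (SD) | Crofelemer arm significant | Arms disagree | ANCOVA rejects |
|---|---|---|---|
| 0 | 4.8% | 9.6% | 5.0% |
| 0.2 | 23% | 37% | 5.0% |
| 0.3 | 46% | 49% | 5.4% |
| 0.5 | 87% | 24% | 4.4% |
| 0.8 | 99.9% | 0.4% | 5.5% |

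The first row shows that, for normal data, the pre-test hardly alters the within-arm error. The last column shows that a between-arm ANCOVA stays near 5% throughout.

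**Step 2: how stable the pre-test is.** If each arm fails Shapiro-Wilk with probability p and the arms share one distribution, they are classified differently with probability 2p(1-p). This cannot exceed 2 × 0.5 × 0.5 = 50%. For normal data it is 2 × 0.05 × 0.95 = 9.5%. Simulated values at 40 per arm:

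| Assumed distribution | Arms classified differently |
|---|---|
| Normal | 9-10% |
| Gamma, shape 8 / 5 / 4 | 44% / 50% / 48% |
| Rounded 0-10 score | 38% |
| Lognormal, sigma 0.5 | 26% |
| Exponential | 1% or less |
| Baseline BSS with the entry floor of 5.0 | about 8-48%, by assumed mean and SD |
| Change in BSS | about 7-12% |
| Counts with about 60% zeros | 0% |

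Some of the BSS and count settings used 1,000 runs. These figures apply only if normality is checked by arm.

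**Step 3: what baseline adjustment buys.** With equal variances, ANCOVA variance is 1-r² times that of an unadjusted between-arm comparison of post values, and (1-r²)/(2(1-r)) times that of a comparison of changes.

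- r = 0.3: 0.91 and 0.91/1.4 = 0.65, so 9% and 35% lower.
- r = 0.5: 0.75 and 0.75/1 = 0.75, so 25% lower for both.
- r = 0.7: 0.51 and 0.51/0.6 = 0.85, so 49% and 15% lower.

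**The case against.** The strongest reply is that the pre-test does little harm. It leaves the within-arm error near 5% for normal data. The one quantity the plan powers is a response proportion, and adequate relief is dichotomous; both go to chi-square or Fisher and bypass the rule. Both statements are correct, and they limit the point to continuous outcomes.

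A reader might infer that the pre-test causes the missing treatment contrast. It does not. If the pre-test were deleted and either paired test kept, there would still be no contrast. Conversely, changing to two-sample tests while keeping the pre-test would leave the effect measure undecided. The two faults are separate.

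A reader might also infer that the arms will receive different tests in about half of trials. The documents do not support that. The unit of testing is not stated. Testing by arm is a natural reading because the tests are paired, but it remains an inference. Figures near 50% lie at the mathematical ceiling and arise for particular shapes. For change in BSS the figure is about that for normal data, and for zero-heavy counts it is nil. Likewise, the entry floor truncates baseline BSS between 5.0 and 7, but this alone does not invalidate a test on change.

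Finally, the variance reductions in Step 3 compare ANCOVA with between-arm tests that the plan does not contain. They support the choice of replacement; they do not measure a loss against the plan's own analysis.

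**Conclusion.** The point holds for continuous outcomes. The written rule leaves the test and summary to the observed data, and neither branch yields a crofelemer-minus-placebo estimate with a confidence interval, contrary to the comparison that B1 sets out. The second fault is the larger.

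Its size depends on how much both arms improve. With no drug effect and a shared 0.3 SD improvement, the crofelemer arm is significant in about 46-47% of trials and the arms disagree in about 49%. This rests on the assumed SD of 1, correlation of 0.5, normal data and 40 per arm. The disagreement falls to 24% at 0.5 SD, but there the crofelemer arm is significant in 87% of trials with no drug effect.

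Instability of the pre-test is a secondary matter. Its size runs from 0 to 50% according to shape, and it counts between arms only if normality is checked by arm. Gross error inflation from the pre-test is not shown.

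**What to change.** In the Data Analysis text, delete the Shapiro-Wilk step and the two paired tests as efficacy analyses, and state the following:

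- Each continuous outcome will be compared between arms at the end of the double-blind phase by ANCOVA, with treatment and the patient's own baseline value as terms. It will be reported as an adjusted mean difference with 95% CI. The double-blind phase is the right limit because both groups receive crofelemer afterwards.
- One between-arm rank-based sensitivity analysis will be fixed in advance and applied to all continuous outcomes.
- For episode counts, one between-arm method will be named in advance. A count model with baseline rate is one option; the rank-based analysis is another if counts are sparse, since a count model may be unstable at 40 per arm.

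The sponsor should also state the diary window that defines each outcome; this point does not require a particular one. Pre-post summaries by arm can stay as description.

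The cost is a few lines of text, written before unblinding, and the loss of freedom to switch tests. No extra patients, visits or data are needed. The same edit answers any separate comment that continuous outcomes lack a between-arm test.

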### B3. DESCRIPTION OF RESEARCH PROTOCOL

#### A. Study Design – Overview, Methods, Procedures

This is a randomized, double-blind, placebo-controlled, parallel group, study is designed to evaluate the efficacy and safety of orally administered crofelemer in patients with diarrhea. The study will consist of a 2-week screening phase, a 4-week double-blind treatment phase, followed by a 4 week open-label extension for both groups.

#### Visit 1

- Informed Consent
- Baseline demographics, medical and treatment history
- Baseline questionnaires via RedCap
- Vitals (height, weight, blood pressure, temperature, heart rate)
- Blood draw for bile acid malabsorption (BAM); mast cell activation, i.e C4, tryptase, histamine; and storing of blood for future studies. BAM is a send-out lab performed by Prometheus Labs. Mast cell activation will be done at a research laboratory at BIDMC.
- Subjects meeting the inclusion and exclusion criteria will enter a screening period of up to 2 weeks during which time subjects will complete daily diary assessment of their bowel symptoms including bowel frequency and use of loperamide via RedCap.
- At the conclusion of the screening period, subjects will be evaluated to determine if they met study entry criteria related to diary compliance, loperamide rescue medication use, and stool consistency (i.e., Bristol Stool Score).

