#### Visit 3 (Week 4)

- Adverse event assessment

- Vitals (weight, blood pressure, temperature, heart rate)
- Blood draw for mast cell activation, i.e C4, tryptase, histamine; and storing of blood for future studies
- Subjects will return their unused study drug to the study team for IP accountability.
- Subjects completing the 4 week double-blind treatment phase will be eligible to enter an open-label extension for 4 weeks during which all subjects will receive crofelemer 125 mg BID.
- Subjects will continue to complete daily diary assessments of their bowel symptoms and use of loperamide during the 4-week treatment period via RedCap.

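### Every test named for continuous outcomes is a within-patient pre/post test, so none of them compares crofelemer with placebo

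*Combined protocol and SAP*

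**What the plan says.** The first objective in section B1 is "To evaluate the clinical response of patients with diarrhea to crofelemer relative to placebo". Section B3.A describes the design: "This is a randomized, double-blind, placebo-controlled, parallel group, study". About 80 patients are allocated 1:1, so 40 per arm.

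The Data Analysis paragraph in section B3.B is the only text on statistical tests. It applies a Shapiro-Wilk test to each continuous variable. Variables judged normal "will be compared pre-and post- interventions using paired Student's t-test". For the rest: "Continuous data which are not normally distributed will be presented as median (range) and compared using Wilcoxon signed-rank test". Proportions are to be compared by chi-square or Fisher exact test, without saying which groups are compared.

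The paragraph does not define the post-intervention time point. Double-blind treatment ends at Week 4, after which completers are "eligible to enter an open-label extension for 4 weeks during which all subjects will receive crofelemer 125 mg BID".

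**The concern.** The question is a difference between two randomised arms. The paired t-test and the signed-rank test ask something else: whether the average change within a set of patients differs from zero. Change within an arm mixes any drug effect with placebo response, natural fluctuation and regression to the mean. Randomisation is there to cancel these, but only if the arms are compared.

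The plan itself gives reason to expect improvement without a drug effect. The Sample Size Justification assumes a 40% placebo response. Inclusion criterion 4 requires a high Bristol Stool Score (BSS) in the week before randomisation, which invites regression to the mean in that score. An analyst who follows the text would produce no treatment difference and no confidence interval for any continuous outcome, and could report a significant improvement on crofelemer that placebo shares. If the post value were taken at Week 8, both arms would be on open-label crofelemer and no concurrent control would exist.

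**Working it through.** **1. Which outcomes are affected.** The Questionnaires/Efficacy Assessments section lists BSS, bowel movements, incontinence episodes, urgency episodes, worst abdominal pain, discomfort, bloating and IBS-QoL. All eight are scores or counts and fall under the continuous-data rule. Weekly adequate relief is dichotomous and falls under the proportions rule.

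**2. Whether another rule fills the gap.** The document contains no two-sample t-test, rank-sum test, ANCOVA or mixed model. The signed-rank sentence does not repeat the pre/post wording, but that test needs pairs, and a crofelemer patient has no paired placebo patient.

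**3. The plan's own figure.** The only figure is 80 patients for 85% power with 40% placebo response. It cannot be reproduced, because the crofelemer response rate, alpha and sidedness are not given. It concerns a proportion, and nothing below depends on it.

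**4. Rejection rate of the paired test with an inert drug.** Inputs: n = 40 (80 at 1:1); two-sided alpha 0.05 (assumed); shared mean improvement of d SDs of change (assumed, as the document gives no SDs). The t statistic is noncentral with 39 degrees of freedom and noncentrality d × √40; the critical value is 2.023. Call the rejection probability p. With the test run separately in two independent arms, the chance that crofelemer is significant and placebo is not is p(1 − p).

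| d | d × √40 | p, crofelemer arm | p(1 − p) | p if both arms are pooled (n = 80) |
|---|---|---|---|---|
| 0.3 | 1.90 | 0.457 | 0.457 × 0.543 = 0.25 | 0.755 |
| 0.4 | 2.53 | 0.694 | 0.694 × 0.306 = 0.21 | 0.942 |
| 0.5 | 3.16 | 0.869 | 0.869 × 0.131 = 0.11 | 0.993 |

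In a simulation of two identical arms of 40, a two-sample t-test on the same changes rejected in 5.0% of trials at d = 0.3 and at d = 0.5.

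**5. Regression to the mean in BSS.** Assume that weekly mean BSS before selection is normal with mean μ and SD σ, that baseline and follow-up have the same variance and correlation ρ, and that entry requires baseline ≥ 5. Let a = (5 − μ)/σ, λ = φ(a)/[1 − Φ(a)] and v = 1 + aλ − λ². With no treatment effect, the expected fall is (1 − ρ)λσ, and the SD of change is σ√[(1 − ρ)²v + 1 − ρ²]. Their ratio is d.

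- μ = 4.8, σ = 0.8, ρ = 0.5: λ = 0.964, v = 0.312; fall 0.385, SD 0.728, d = 0.53; paired test significant in about 90%.
- μ = 5.0, σ = 0.8, ρ = 0.7: λ = 0.798, v = 0.363; fall 0.191, SD 0.589, d = 0.32; about 52%.
- μ = 5.5, σ = 0.8, ρ = 0.7: λ = 0.447, v = 0.521; fall 0.107, SD 0.597, d = 0.18; about 20%.

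Over μ 4.8 to 5.5, σ 0.8 to 0.9 and ρ 0.5 to 0.7, the range is about 20% to 90%. All three inputs are assumed.

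**The case against.** The strongest reply is that the comparison that matters is not affected. The objective speaks of clinical response, the sample size rests on a response rate, adequate relief is dichotomous, and proportions get a test that can compare arms. This stands in part. A reader might infer that the whole trial discards its randomisation or has no test against placebo. The document does not support that: the outcome type on which the trial was sized has a suitable test, even though the groups are not named. Equally, no primary endpoint is named, so the document does not show that the eight continuous outcomes are secondary.

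A second reply is that paired tests have legitimate uses, such as describing change in blood markers between Visits 1 and 3 or change during the open-label weeks. That is fair. The fault is the missing between-arm analysis, not the presence of within-patient summaries.

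A third is that the comparison with placebo is implied, for example by testing each arm and setting the two results side by side. The document states no such decision rule. If it were used, an inert drug would appear to succeed in 25%, 21% or 11% of trials at the three assumed improvements, so it would not repair the problem.

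Finally, the numbers depend on assumptions. This is right, above all for regression to the mean. A reader might infer that the BSS entry rule alone makes a false positive near certain, but the rate falls to 20–35% at an assumed pre-selection mean of 5.5. The rule also selects on BSS, so the calculation does not carry over directly to pain, bloating, incontinence or IBS-QoL.

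**Conclusion.** Wrong as written, for continuous outcomes only. The named tests cannot estimate or test crofelemer against placebo on any of the eight continuous measures. That conclusion follows from the text and needs no numerical assumption.

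The size is illustrative. With an inert drug and 40 patients in the arm, the nominal 5% error becomes 46%, 69% or 87% if both arms improve by 0.3, 0.4 or 0.5 SD of change. Regression to the mean adds to this for BSS by an amount the document does not allow one to fix.

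The case for adjusting for baseline should not be oversold either. A reader might expect the textbook 25% saving in variance at a correlation of 0.5. Among patients selected on BSS, the model in step 5 gives a saving against change scores of 1 − (1 − ρ²)/[(1 − ρ)²v + 1 − ρ²]. That is 1 − 0.75/0.841 = 11% at μ = 5.0, ρ = 0.5, and 1 − 0.51/0.538 = 5% at μ = 4.8, ρ = 0.7. The reason for the change is to obtain the right comparison; the precision is a small bonus.

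**What to change.** For each continuous outcome, replace the paired test as the efficacy analysis with a between-arm comparison over the double-blind period. Use the diary mean over Weeks 1–4, or the Week 4 IBS-QoL, in an ANCOVA or mixed model with treatment and the patient's own baseline. Report the crofelemer minus placebo difference with its 95% CI. State which screening days or visit supply the baseline.

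For skewed outcomes, give a rank-based between-arm test (rank-sum or rank ANCOVA) as a sensitivity analysis instead of the signed-rank test.

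Keep within-patient pre/post results, including those from open-label Weeks 5–8, as descriptive, and say that they are not evidence of efficacy against placebo.

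The cost is a revised paragraph and a little more analysis. The daily diary already runs from screening onward and IBS-QoL is already scheduled at every visit, so no extra data are needed.

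### Continuous outcomes are analysed only by paired pre/post tests and no analysis set or denominator is defined, so arms are not compared on these outcomes and a completer analysis is not prevented

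*Combined protocol and SAP*

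**What the plan says.** The Data Analysis paragraph in B3.B is the whole analysis plan. After a normality test, continuous variables "will be compared pre-and post- interventions using paired" t-test, or by Wilcoxon signed-rank if not normal. For binary outcomes, "Proportions will be expressed as percentages and compared using chi-square test or fisher exact test as appropriate".

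The Sample Size Justification reads: "This study aims to recruit 120 subjects until 80 subjects are enrolled". It adds: "This sample size is based on a 85% power calculation assuming placebo response is 40" per cent. At Visit 2, "Approximately 80 patients will be randomly assigned (in a 1:1 ratio") to the two arms. The design is "a 4-week double-blind treatment phase, followed by a 4 week open-label extension for both groups".

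Most efficacy data are patient-entered. B3.A (Questionnaires/Efficacy Assessments) has a daily diary of stool, pain, discomfort and bloating scores, and a weekly binary item: "Once per week patients will be asked whether they have experienced adequate relief of their diarrheal symptoms".

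The documents define no analysis set, no rule for missing diary days or withdrawals, no sensitivity analysis and no allowance for drop-out after randomisation. The diary-completion thresholds in inclusion criterion 5 apply only before randomisation. The step from 120 to 80 comes before enrolment and reads as a screening allowance.

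**The concern.** The first primary objective in B1 is response to crofelemer relative to placebo. A paired test answers a different question, namely whether patients changed from before to after. It needs both values from the same patient, so anyone without a post value is excluded by construction. It also takes one post value per patient, so the course of a daily diary over four weeks is either collapsed or left unused.

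For proportions, the plan does not say whether the denominator is everyone randomised or only those who answered. That choice could be made after the data are seen. Patients without relief have an obvious reason to stop the diary or leave. If this happens more in one arm, a comparison of completers can show a difference where none exists, in either direction.

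**Working it through.** **Inputs from the documents.** About 80 randomised 1:1, so 40 per arm; placebo response 40%; power 85%.

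**Inputs assumed, because the documents give none.** Two-sided alpha 5%; drop-out 10% to 25%; pooled chi-square without continuity correction.

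**1. The plan's own figure.** The 85% cannot be reproduced directly, because the crofelemer rate, alpha and sidedness are missing. It can only be solved backwards. Exact power is the sum of Bin(x; n, p1) × Bin(y; n, p2) over all tables with pooled |z| ≥ 1.96. With n = 40, p1 = 0.40 and p2 = 0.72 this gives 84.7%, so about 72% is one rate that fits. The normal-approximation formula gives 72.6% two-sided and 69.3% one-sided.

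**2. Bias when loss depends on outcome and differs by arm.** Take a true response of 40% in both arms, so 16 of 40 respond in each, and let all drop-outs be non-responders. The expected completer rate is 16 / [40 × (1 − d)].

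| Loss, placebo / crofelemer | Placebo completers | Crofelemer completers | Spurious difference | Type I error |
|---|---|---|---|---|
| 10% / 10% | 16/36 = 44.4% | 16/36 = 44.4% | 0 | 5.2% |
| 10% / 20% | 16/36 = 44.4% | 16/32 = 50.0% | +5.6 points | 7.6% |
| 10% / 25% | 16/36 = 44.4% | 16/30 = 53.3% | +8.9 points | about 11% |

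Type I error is by simulation (400,000 trials), each non-responder leaving with probability d / 0.60. With no loss the test itself runs at 5.2%, so equal loss adds nothing. Exchanging the arms reverses the sign. With everyone randomised in the denominator and drop-outs counted as no relief, each row returns to 16/40 versus 16/40.

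**3. Completer power depends on what is assumed** (exact enumeration).

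| Scenario | 0% loss (40/arm) | 10% loss (36/arm) | 15% loss (34/arm) |
|---|---|---|---|
| 40% vs 72%, loss unrelated to response | 84.7% | 78.7% | 76.7% |
| 40% vs 75%, loss unrelated to response | 90.7% | 86.3% | 84.9% |
| 40% vs 72%, equal loss, all non-responders | 84.7% | about 90% | about 93% |

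In the last row the completer rates at 10% loss are 0.40/0.90 = 44.4% and 0.72/0.90 = 80.0%. Power can therefore fall below 85%, stay near it or rise above it.

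**4. Power when missing counts as no relief.** If loss d is unrelated to response, both rates are multiplied by (1 − d) and n stays at 40 per arm. For 40% versus 72%:
- d = 10%: 36.0% versus 64.8%, power 76.1%
- d = 15%: 34.0% versus 61.2%, power 71.3%

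**The case against.** The best defence is that much of this is silence, not a stated choice. Several parts of it stand.

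- **Proportions.** A reader might infer that relief percentages are taken only over those who answered. The plan does not say so. Chi-square and Fisher tests run equally well on all randomised patients with drop-outs counted as non-responders.
- **The post value.** A reader might infer that every patient without a Week 4 value is dropped. The plan does not define post as Week 4. With a daily diary, someone who leaves in Week 2 may still supply a post value. Only a patient with none is excluded by construction.
- **Power.** A reader might infer that power is below 85%. The documents cannot show this: a planned rate of 75% would leave slack at 10% loss. The power statement also concerns a response proportion, so the paired tests do not bear on it.
- **Size of the bias.** The inflated error rates need one arm to lose at least twice what the other loses, with every drop-out a non-responder, within four weeks. They are illustrations, not forecasts.

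The defence does not reach the continuous outcomes. There the method is stated, and it is a within-patient pre/post test. No other section supplies a between-arm analysis, an analysis set or a missing-data rule for them.

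**Conclusion.** The point holds in limited form. The stated method for continuous outcomes excludes patients without a post value, uses one post value each and makes no comparison with placebo. For proportions, the open denominator leaves a completer analysis available without prescribing it.

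Under the assumed 10% versus 20% loss, all non-responders, the choice of denominator moves a null result from 0 to +5.6 points and the type I error to about 7.6%. Under equal loss it does not matter for bias. The stated 85% power is unverified under any attrition. It is not shown to be too high, because effect size, alpha, sidedness and drop-out are all unstated.

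The plan should be changed before the data are analysed.

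**What to change.** In Data Analysis (B3.B):

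1. State that all randomised patients are analysed in the arm to which they were assigned.
2. For daily scores, replace the paired tests with a between-arm, likelihood-based repeated-measures model over Weeks 1–4 of the double-blind phase, with baseline as covariate. Patients with partial diaries then contribute what they recorded. The model assumes that missingness is explained by the observed data. Other between-arm methods that keep partial data would also serve.
3. For adequate relief, make everyone randomised the denominator and count a week with no answer, or after withdrawal, as no relief. Report completers as a sensitivity analysis.

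In Sample Size Justification, state the assumed crofelemer rate, alpha, sidedness and drop-out, and the power that results under the rule in item 3.

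The cost is a few sentences and slightly more modelling, with no new visits or data. The real downside is power: if drop-out is unrelated to response, item 3 takes 40% versus 72% with 40 per arm from 85% to about 76% at 10% loss and 71% at 15%. Item 3 guards against the completer bias shown above; it does not restore power. If the resulting figure is too low, the number randomised has to be reconsidered.
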